APPENDIX A: Schedule of Treatment and Evaluations

	Screening -21 Days	Cycle 1	Cycle 2	Cycle 3	Cycle 4	Cycle 5	Cycle 6	End of Treatment ¹⁴	Every 2 or 3 mo. ¹³	Follow Up ¹²
Signed informed consent	X									
Review inclusion/exclusion	X	X								
Medical history ¹	X									
Physical examination	X	X	X	X	X	X	X	X ¹⁶	X	
Height (cm)	X									
Weight (kg)	X	X	X	X	X	X	X			
BSA calculation ²		X	X	X	X	X	X			
Vital signs ³	X	X	X	X	X	X	X	X	X	
ECOG PS	X	X	X	X	X	X	X	X		
CT/ MRI scan / tumor measurements ⁴	X ^{8a}			X ⁸		X ⁸		X ¹⁰	X	
ECG	X	X	X	X	X	X	X	X ¹¹	X	
ECHO (with ejection fraction) or MUGA/cardiac ultrasound	X		X		X		X	X	X	
CBC w/differential & plts ⁵	X	X ¹⁶	X	X	X	X	X	X ¹¹	X	
Coagulation tests (PT, PTT, INR)	X									
Serum chemistries ^{5, 6}	X	X ¹⁶	X	X	X	X	X	X ¹¹		
Urinalysis ⁷	X							X ¹¹		
Serum troponin	X	X ¹⁶	X	X	X	X	X	X ¹¹	X	
Serum/urine pregnancy test	X									
Randomization		X ¹⁵								
INNO-206 or doxorubicin admin administration ¹⁷		X	X	X	X	X	X			
Blood alcohol level ¹⁸		X	X	X	X	X	X			
Concomitant medications	X ⁹	X	X	X	X	X	X	X		
Adverse events	X	X	X	X	X	X	X	X		
Telephone call										X

NOTE: All assessments must be performed within 72 hr of each specified time parameter, except Cycle 1 (see Section 7 for details).

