1. SYNOPSIS

Name of Sponsor/Company: CytRx Corporation	
Protocol Number: INNO-206-P2-STS-01	Phase of Development: 2b
Title of the Protocol: A Multicenter, Randomized, Open-Label Phase 2b Study to Investigate the Preliminary Efficacy and Safety of INNO-206 (Doxorubicin-EMCH) Compared to Doxorubicin in Subjects with Metastatic, Locally Advanced, or Unresectable Soft Tissue Sarcoma	
Primary Objectives: The primary objective of this study is to determine the preliminary efficacy of administration of INNO-206 compared to doxorubicin in subjects with metastatic, locally advanced, or unresectable soft tissue sarcoma as measured by progression-free survival, progression-free survival at 4 and 6 months, tumor response and overall survival.	
Secondary Objectives: The secondary objective of this study is to evaluate the safety of INNO-206 compared to doxorubicin in this population assessed by the frequency and severity of adverse events (AEs), abnormal findings on physical examination, laboratory tests, vital signs, multiple-gated acquisition (MUGA) scans/cardiac ultrasound evaluations, electrocardiogram (ECG) results, and weight.	
Study Rationale and Significance: INNO-206 is a novel prodrug that binds covalently to albumin in the circulation. The drug is accumulated in tumors and doxorubicin is released in the tumor by cleaving the acid labile linker (EMCH) in the low pH tumor environment. This carrier-linked prodrug has demonstrated enhanced anti-tumor activity with reduced toxicity in several murine models when compared with free doxorubicin. Patients with metastatic, locally advanced, or unresectable soft tissue sarcomas have a poor prognosis with progression-free survival of around 4-5 months and median overall survival of approximately 15 months. Three-year survival rates as high as 30% have been observed in some clinical studies. Several chemotherapy regimens have been explored as palliative therapy for subjects with advanced soft tissue sarcomas. Combinations of ifosfamide and doxorubicin appear to offer the highest response rates and longest time to progression. However, these regimens are quite toxic and have not significantly increased survival in these individuals. INNO-206 may improve the activity of doxorubicin without increasing its toxicity as has been demonstrated in animal studies.	

Name of Sponsor/Company: CytRx Corporation	
Protocol Number: INNO-206-P2-STS-01	Phase of Development: 2b

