
Study Design and Methodology: This is a phase 2b open-label study evaluating the preliminary efficacy and safety of INNO-206 administered at 350 mg/m² (260 mg/m² doxorubicin equivalent) intravenously (IV) on Day 1 every 21 days for up to 6 consecutive cycles compared to doxorubicin administered at 75 mg/m² for up to 6 consecutive cycles. Subjects will be randomized 2:1 to receive either INNO-206 or doxorubicin.
 
Subjects will visit the study site every 21 days for their IV infusions, at which time safety monitoring, including AEs, a directed physical examination, laboratory evaluations (serum chemistry, complete blood count [CBC], and urinalysis), vital signs, weight measurements, ECOG performance status and ECGs will be performed. Cardiac function will also be followed periodically using either MUGA scans or cardiac ultrasounds. Treatment will continue every 21 days until tumor progression is observed, 6 cycles of treatment are completed or unacceptable toxicity occurs.
 
Tumor response will be monitored every 6 weeks from Cycle 1-Day 1 during treatment, at End of Treatment, 2 months following the End of Treatment scan (for those subjects completing 6 cycles), and then every 3 months until disease progression using the Response Evaluation Criteria in Solid Tumors (RECIST) 1.1 criteria. For those subjects that leave the study prior to completing Cycle 6, and who do not start another therapy, they can be followed 2 months following the End of Treatment scan, and then every 3 months until disease progression. However, if a subject receives another therapy, they should only be followed for overall survival [OS]. Progression-free survival [PFS], progression-free survival at 4 and 6 months and OS will be monitored as other primary objectives.
	

Name of Sponsor/Company: CytRx Corporation	
Protocol Number: INNO-206-P2-STS-01	Phase of Development: 2b

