
Name of Sponsor/Company: CytRx Corporation	
Protocol Number: INNO-206-P2-STS-01	Phase of Development: 2b

11. Current, serious, clinically significant cardiac arrhythmias, defined as the existence of an absolute arrhythmia or ventricular arrhythmias classified as Lown III, IV or V.
 
12. Baseline QTc >470 msec and/or previous history of QT prolongation while taking other medications. Concomitant use of medications associated with a high incidence of QT prolongation is not allowed
 
13. History or signs of active coronary artery disease with or without angina pectoris.
 
14. Serious myocardial dysfunction defined as scintigraphically (eg MUGA, myocardial scintigram) or ultrasound determined absolute left ventricular ejection fraction (LVEF) <45% of predicted.
 
15. History of HIV infection.
 
16. Active, clinically significant serious infection requiring treatment with antibiotics, anti-virals or anti-fungals.
 
17. Major surgery within 3 weeks prior to Randomization.
 
18. Substance abuse or any condition that might interfere with the subject's participation in the study or in the evaluation of the study results.
 
19. Any condition that is unstable and could jeopardize the subject's participation in the study.
	

Number of Subjects: One hundred and five (105) study subjects will be randomized 2:1 (INNO-206:doxorubicin) at approximately 30 study centers in the United States (US), Hungary, Romania, Ukraine, Russia, India, and Australia. Up to 32 subjects may be enrolled in India, with the remaining subjects distributed in the other locations.
	

Test Product, Dose and Mode of Administration: Lyophilized powder in vials that contain 200 mg of INNO-206 reconstituted by adding a solution of 50% ethanol: 50% sterile water, administration completed within 2 hours (of being reconstituted) as a 30 minute IV infusion in Lactated Ringer's solution. Total dose of 350 mg/m² (260 mg/m² doxorubicin equivalent).
	

Reference Therapy, Dose and Mode of Administration: Doxorubicin HCl Injection is a sterile parenteral, isotonic available in 5 mL (10 mg), 10 mL (20 mg), 25 mL (50 mg) single dose vials. Each mL contains doxorubicin HCl and the following inactive ingredients: NaCl (0.9%) and water for injection q.s. Hydrochloric acid is used to adjust the pH to a target of pH of 3.0. Prepare IV infusion per the package insert (see the Study Reference Manual).
	

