
Criteria for Evaluation:
 
Efficacy: The following efficacy variables will be evaluated as noted:
 
 • Progression-free survival • Overall survival • Objective tumor response (RECIST 1.1 criteria) • 4 and 6 month progression-free survival 
Safety: The following safety variables will be assessed over the duration of the study:
 
 • Adverse events • Ability to remain on assigned treatment (tolerability) • Clinical and laboratory data including physical examinations, vital signs, weight, MUGA/cardiac ultrasound evaluations, ECG results and laboratory test results • Use of concomitant medications 	

Name of Sponsor/Company: CytRx Corporation	
Protocol Number: INNO-206-P2-STS-01	Phase of Development: 2b

Statistical Methods: In accordance with the intention-to-treat principle, all randomized subjects who enter active treatment and have had at least 1 dose of study medication and 1 post-dose efficacy measurement will be included in the primary statistical analyses according to the treatment group to which they were originally assigned.
 
Efficacy: Tumor response will be monitored every 6 weeks from Cycle 1-Day1 during treatment, at End of Treatment, 2 months following the End of Treatment scan (for those subjects completing 6 cycles), then every 3 months until disease progression. For the estimation of progression-free and overall survival a Kaplan-Meier analysis will be performed. The percentage of subjects with complete or partial responses, or stable disease will be evaluated at 4 and 6 months.
 
Safety: The safety data will be summarized by treatment group. The treatment groups will be compared with respect to occurrence of each AE. Total number of AEs leading to withdrawal, and abnormal laboratory tests will be compared between groups using Fisher’s exact test. Adverse events, ability to remain on assigned treatment (tolerability), and abnormal findings on physical examinations, vital signs, weight, ECG results, laboratory test results, and use of concomitant medications, will be assessed to characterize the safety profile of the treatment regimens. Descriptive statistics denoting the changes from baseline to the final assessment visit with respect to key laboratory parameters and vital signs will also be provided.
	

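### Troponin and CBC testing appears to stop at progression or new therapy, so an unadjusted Fisher's exact test can make the arm with longer PFS look more toxic

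*Combined protocol and SAP*

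**What the plan says.** References are to Amendment 2 (April 15, 2012), the latest text supplied.

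- **Schedule (Appendix A).** The rows "Serum troponin" and "ECHO (with ejection fraction) or MUGA/cardiac ultrasound", with CBC and ECG, are marked during treatment, at End of Treatment and in the column for visits every two or three months. Adverse events and serum chemistries have their last mark at End of Treatment. The only item under Follow Up is a telephone call.
- **Length of treatment (Synopsis, Study Design and Methodology).** "Treatment will continue every 21 days until tumor progression is observed, 6 cycles of treatment are completed or unacceptable toxicity occurs". Six cycles of 21 days is 126 days.
- **Length of the later visits (same section).** Tumour response is assessed two months after the End of Treatment scan, "and then every 3 months until disease progression using the Response Evaluation Criteria in Solid Tumors (RECIST) 1.1 criteria". Subjects who start another therapy are followed for overall survival only. Those who stop early without new therapy may be followed, but the wording is permissive.
- **Safety analysis (Synopsis, Criteria for Evaluation and Statistical Methods).** Safety variables are assessed for as long as the study lasts. AE occurrence is compared by arm. "Total number of AEs leading to withdrawal, and abnormal laboratory tests will be compared between groups using" Fisher's exact test. Kaplan-Meier is named for PFS and overall survival only. MUGA/cardiac ultrasound is a listed safety variable, but the safety methods name no between-arm analysis for it.

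**The concern.** If the later visits end at progression or new therapy, a subject whose disease is controlled longer has more troponin and CBC tests over a longer time, and so more chance of an abnormal result. Fisher's test on the proportion ever abnormal treats all subjects as observed equally.

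The synopsis hopes for more activity than doxorubicin without more toxicity. If the first half of that is true, the unadjusted comparison works against the second: success on PFS could produce an apparent laboratory safety signal with no difference in risk. Both arms deliver an anthracycline, so troponin is a result readers will look at.

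**Working it through.** **Inputs from the documents.** 105 subjects randomized 2:1, so 105 × 2/3 = 70 on INNO-206 and 105/3 = 35 on doxorubicin. Background: "poor prognosis with progression-free survival of around 4-5 months"; I use 4.5 months and show 4 to 5. The supplied text gives no abnormality rate, PFS effect or power statement, so there is no plan figure to reproduce.

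**Assumptions.** Monthly risk of a first abnormality h = 0.01 to 0.04, the same in both arms. PFS hazard ratio 0.5 to 1. PFS exponential.

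**Step 1, closed form.** With constant h and progression hazard L = ln 2 / median, the proportion ever abnormal before testing stops is h/(h + L). For a control median of 4.5 months, L = 0.154 per month. With h = 0.02:

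| PFS HR | L | Proportion abnormal | Ratio to control |
|---|---|---|---|
| 1 (control) | 0.154 | 0.02/0.174 = 11.5% | 1 |
| 0.75 | 0.1155 | 0.02/0.1355 = 14.8% | 1.28 |
| 0.5 | 0.077 | 0.02/0.097 = 20.6% | 1.79 |

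Over control medians of 4 to 5 months and h of 0.01 to 0.04, the ratio is 1.24 to 1.31 at HR 0.75 and 1.63 to 1.90 at HR 0.5.

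**Step 2, simulation on a visit schedule.** 35 v 70 subjects, 800 replicates per scenario, no true difference in risk. Tests were at days 21, 63, 105, 126 and 186, then every 91 days, stopping at progression. This is the imaging timetable; troponin and CBC are tested more often on treatment but at the same visits afterwards. The constant-risk scenario uses h = 0.02. The other two use 0.06 per month, only after day 126 or only up to day 126.

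| Risk pattern | PFS HR | Crude ratio | Fisher rejects | Person-time rate ratio | Log-rank rejects |
|---|---|---|---|---|---|
| Constant | 0.75 | 1.24 | 4.0% | 0.99 | 3.7% |
| Constant | 0.5 | 1.74 | 16.4% | 1.03 | 5.2% |
| Only after day 126 | 0.75 | 1.34 | 9.0% | 1.11 | 6.2% |
| Only after day 126 | 0.5 | 1.98 | 42.7% | 1.29 | 3.9% |
| Only to day 126 | 0.75 | 1.05 | 5.1% | 0.81 | 5.0% |
| Only to day 126 | 0.5 | 1.11 | 3.6% | 0.61 | 5.5% |

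At constant risk and HR 0.5, the mean number of tests per subject was 5.0 on control and 7.5 on INNO-206. When progression and abnormality shared a frailty, log-rank rejected in 5.1% to 6.1% of trials.

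**Step 3, which remedies work.** Cumulative incidence with progression as a competing event is h/(h + L) × (1 − exp(−(h + L)t)). As t grows this tends to h/(h + L), the crude figure of Step 1. With h = 0.01 and medians of 4.5 v 8 months (an assumed HR of 4.5/8 = 0.56):

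- 12 months: 5.2% v 7.1%, ratio 1.35
- 24 months: 6.0% v 9.3%, ratio 1.56
- limit: 6.1% v 10.3%, ratio 1.70

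So this method reproduces the distortion. The person-time rate is right when risk is constant but ran from 0.61 to 1.29 with no true difference, and its test rejected in 20% of trials with early risk at HR 0.5. Stopping the same formula at 126 days (4.14 months) gives 3.0% v 3.4%, a ratio of about 1.13, so a fixed window removes most of the distortion. Log-rank with censoring at the last test stayed near its nominal 5% in all these patterns.

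**The case against.** The strongest case against has four parts.

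1. **The stopping rule is inferred.** The progression limit is written for tumour response. The footnotes that define the later visit columns are not in the supplied text, and only synopses and schedules are available. This stands as a limit on certainty. The inference is still strong, because the cardiac and laboratory marks sit in the same visit column and nothing but a telephone call follows it.
2. **The scope is narrow.** A reader might infer that all safety comparisons, or a crude ECHO/MUGA comparison, are distorted. The documents do not support that. AEs and serum chemistries end at End of Treatment, where observation is capped and the distortion small. Fisher's test is named for AEs leading to withdrawal and for abnormal laboratory tests, so among the items tested later it reaches troponin and CBC. For imaging, the gap is that no analysis is named. This part stands.
3. **The size depends on a large PFS benefit and lasting risk.** At HR 0.75 with constant risk, Fisher's false rejection was 4.0%, no more than nominal, although the estimate was still shifted. This stands.
4. **Part of a crude excess may be real.** Longer PFS can mean more cycles and a higher cumulative dose, and a correction for time should not hide that. This also stands, and is a reason to report exposure by arm.

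None of this removes the point that the stated comparison takes no account of unequal observation.

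**Conclusion.** The concern holds in a limited form, as an inexpensive improvement. The planned Fisher comparison of abnormal laboratory tests can overstate troponin and CBC abnormality in the arm with longer PFS. Under equal, constant risk the crude ratio is about 1.3 at a PFS HR of 0.75 and 1.6 to 1.9 at 0.5. It is 1.05 to 1.11 if risk is confined to treatment. These figures rest on assumed hazards and PFS effects, and on later testing ending at progression; new therapy as a further stopping point was not modelled.

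A reader might also infer that any time-at-risk analysis corrects the problem. It does not: competing-risk cumulative incidence tends to the crude figure, and a person-time rate can err in either direction. Nor can any analysis of the scheduled data recover abnormalities that arise after testing stops, and that gap is larger in the arm with shorter PFS.

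**What to change.** Specify the following for troponin and CBC abnormalities, and for cardiac imaging if it is compared between arms. Do so before PFS by arm is known, since the trial is open-label.

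- **Fixed window.** Compare within a window common to both arms, for example through End of Treatment. Define it by days from randomization, because the End of Treatment visit itself comes earlier in subjects who progress.
- **Time to event.** Compare time from randomization to first abnormality, censored at the last test, by log-rank or cause-specific hazard.
- **Not as the correction.** Do not rely on cumulative incidence with progression as a competing event, or on a simple person-time rate.
- **Context by arm.** Report number of assessments, subject-months observed and cumulative dose. Keep crude percentages as description only.
- **Limits.** State when the later tests end, and that abnormalities after that point are unobserved.

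The cost is a little more analysis work on data already scheduled. The fixed window leaves out later abnormalities, which is why the time-to-event comparison goes with it. No tests are added and clinical monitoring does not change.
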